#### **8.4 Post-operative Follow-up Visits (Day 1 to Last Study Visit)**

Subjects will have standard of care assessments throughout the study according to the hospital/institutions standard procedures as well as study specific visits on postoperative Day 1, the date of discharge, Week 8 (56 ±14 days) and the date of ileostomy closure, if applicable. Subjects will be assessed for the following throughout the study:

- Serum hemoglobin measurement (Day 1).
- Evidence of anastomotic leak.
- Assessment and grading of post-operative complications.
- Concomitant medications and procedures as described in Section 7.2.
- Adverse events according to Section 9.

Although the patient may be seen by various individuals post-surgery, the study-specific visits must be conducted by a surgeon who is part of the study and has signed the Signature and Delegation Log. Any complications and outcomes of study required assessments between visits will be documented at the study required visits.

Subjects with a discharge date later than Week 8, who did not have an ileostomy, will have the last study visit on Week 8 ±14 days.

Diverted patients should receive routine endoscopic and/or contrast enema evaluation of the anastomotic region, between 3 weeks post-surgery and the Week 8 visit.

Subjects who present with a clinical suspicion of anastomotic leak during the study will have a CT scan with PO and, if necessary (e.g., presence of a diverting ileostomy), rectal contrast to confirm.

## **8.5 Image Acquisition and Transmission**

Videos of the image sequences acquired using PINPOINT and SPY Elite will be recorded to a medical grade video recorder. All required images will be provided to the Sponsor by the Investigative Center. Image files will be identified using the subject I.D. number and initials only (no information identifying the subject shall be included in the files).

## **9 EVALUATION, RECORDING, AND REPORTING OF ADVERSE EVENTS**

All untoward medical occurrences either observed by the Investigator or one of his/her medical collaborators, or reported by the subject spontaneously, or in response to the direct question below, will be reported as follows:

- All events occurring before randomization should be recorded in the source documents and will be considered part of the subject's case history.
- Events occurring as a result of the surgery will be reported as adverse events related to the surgical procedure in the adverse event CRF.
- All adverse events occurring during the study will be recorded as adverse events on the adverse event CRF.
- Events related to the use of PINPOINT or SPY Elite will be recorded as adverse device effects in the description of event section of the adverse event CRF.
- Events related to PINPOINT or SPY Elite that affect a user of the device (non-patient) are recorded on the technical complaint form.

In an attempt to optimize consistency of AE reporting across centers, the subjects must be asked a standard question to elicit events. At each clinic evaluation of the subject, study personnel will ask the following questions: "Have you had any problems since your last visit?"

AEs reported on the CRF will include the date of onset, severity, relationship to PINPOINT or SPY Elite, relationship to surgical procedure, date of resolution (or the fact that it is ongoing or has become chronic), action taken, and whether the AE is serious or not.

### **9.1 Definitions**

#### **9.1.1 Adverse Event (AE)**

Any untoward medical occurrence, unintended disease or injury or any untoward clinical signs (including an abnormal laboratory findings) in subjects whether or not related to the investigational medical device.

- Includes events related to the PINPOINT or SPY Elite.
- Includes events related to procedures involved (any procedure in the clinical investigation plan).
- Postoperative nausea or vomiting occurring during the first 24 to 48 hours, and post-

operative pain related to surgical procedure is not considered an adverse event.

#### 9.1.2 Adverse Device Effect (ADE)

Any adverse event related to the use of PINPOINT or SPY Elite (includes imaging agent and all hardware components).

- Includes any event that is a result of a use error or intentional misuse.

ADEs that affect subjects will be recorded as ADEs in the AE CRF. ADEs that only affect a user (non-patient) are recorded in the technical complaint form only.

#### 9.1.3 Serious Adverse Event (SAE)

Any adverse event that:

- a. Led to a death.
- b. Led to a serious deterioration in health that either:
  - i. Resulted in a life-threatening illness or injury,
  - ii. Resulted in a permanent impairment of a body structure or a body function,
  - iii. Required in-patient hospitalization or prolongation of existing hospitalization,
  - iv. Resulted in medical or surgical intervention to prevent life threatening illness or injury or permanent impairment to a body structure or a body function.
- c. Led to fetal distress, fetal death or a congenital abnormality or birth defect.

This includes device deficiencies that might have led to a serious adverse event if suitable action had not been taken; intervention had not been made, or if circumstances had been less fortunate. These are handled as SAEs. A planned hospitalization for pre-existing condition, or a procedure required by the protocol, without a serious deterioration in health, is not considered to be a serious adverse event.

#### 9.1.4 Unanticipated Adverse Device Effect (UADE)

Any ADE that meets the following:

- By its nature, incidence, severity or outcome has not been identified in the current version of the PINPOINT (or SPY Elite if applicable) risk analysis report.
- On health or safety, any life-threatening problem or death caused by, or associated with a device, if that effect, problem, or death was not previously identified in nature, severity, or degree of incidence in the application; or any other unanticipated serious problem associated with a device that relates to the rights, safety, or welfare of subjects.

## 9.2 Adverse Event Descriptions

### 9.2.1 Intensity

The intensity of AEs, including ADEs and surgical complications will be characterized as mild, moderate, or severe, as follows:

Mild	Usually transient, requiring no special treatment, and does not interfere with the subject's daily activities.
Moderate	Introduces a low level of inconvenience or concern to the subject and may interfere with daily activities, but is usually ameliorated by simple therapeutic measures.
Severe	Significantly interferes with a subject's usual daily activities and requires systemic drug therapy or other treatment, if available.

### 9.2.2 Relationship

Suspected	There is a reasonable possibility that the AE is associated with use of the study device, such as temporal relationship of the event to use.
Not suspected	A relationship between the AE and the study device can reasonably be ruled out based on lack of any temporal relationship of the event to use, or when the subject's underlying condition, medical history, or other therapy provide sufficient explanation for the observed event.

## 9.3 Reporting and Evaluation of Serious Adverse Events and Unanticipated Adverse Device Effects

Any SAE or UADE occurring in this study must be reported immediately (within 24 hours of discovery) by email to the Novadaq contact listed below:

## 9.4 Surgical Complications: Special Instructions

Anastomotic leaks, and strictures or abscesses that require intervention should be reported and followed as SAEs for this study.

Subjects who present with a clinical suspicion of anastomotic leak during the study will have a computerized tomography (CT) scan to confirm unless the patient’s condition warrants urgent operative intervention. A leak is considered confirmed if endoluminal contents (air, gastrointestinal contents or contrast material) through the anastomosis occur. The presence of infection or abscess thought to be related to the anastomosis may be classified as an anastomotic leak at the surgeon’s discretion even if it cannot be definitively identified as visualized during an operation or by contrast extravasation. An abscess adjacent to the anastomosis containing air will be classified as a leak. All Anastomotic leaks will be followed until resolution.

Specific post-operative complications are defined as follows for this study and should be reported as surgical complications and SAEs if they meet SAE criteria at the time of the event:

- Prolonged post-operative NPO or nasogastric tube (NGT) use is defined as prolonged NPO status or NGT use for more than 3 post-operative days (POD4 or later), or the return to NPO status or insertion(or presence) of NGT anytime POD4 or later within 30 days.
- Post-operative ileus is defined as insertion or reinsertion of a NGT after surgery or a return to NPO status for nausea and/or vomiting with failure of passage of flatus and/or stool.
- A small bowel obstruction is defined as radiologic or operative evidence of an obstruction.

All adverse events and post-operative complications occurring during the study period will be graded according to the following Clavien-Dindo classification system^20 as shown in Table 2. Grades will be recorded on the CRF.

**TABLE 2. Classification of Surgical Complications**

Grade	Definition	Clinical Example of Complication Grade
Grade I	Any deviation from the normal post-operative course without the need for pharmacological treatment or surgical, endoscopic, and radiological interventions	Non-infectious diarrhea
Grade II	Requiring pharmacological treatment with drugs other than such allowed for grade I complications. Blood transfusions and total parenteral nutrition are also included.	Infectious diarrhea requiring antibiotics
Grade IIIa	Requiring surgical, endoscopic or radiological intervention not under general anesthesia	Radiologic or endoscopic intervention of an anastomotic leak that is taken care of outside of the operating room
Grade IIIb	Requiring surgical, endoscopic or radiological intervention under general anesthesia	Surgical intervention of an anastomotic leak that is taken care of in the operating room
Grade IVa	Life-threatening complication (including CNS complications) a requiring IC/ICU management with single organ dysfunction (including dialysis)	Necrotizing pancreatitis
Grade IVb	Life-threatening complication (including CNS complications) a requiring IC/ICU management with multi organ dysfunction	Necrotizing pancreatitis with hemodynamic instability
Grade V	Death of a patient	Organ failure after surgical intervention-
Suffix "d"	If the patient suffers from a complication at the time of discharge, the suffix "d" (for disability) is added to the respective grade of complication. This label indicates the need for a follow-up to fully evaluate the complication.	

a Brain hemorrhage, ischemic stroke, subarachnoidal bleeding, but excluding transient ischemic attacks

## 9.5 Follow-up for Adverse Events and Adverse Device Effects

Throughout the study to the final study visit contact, ADEs will be followed until they resolve or become chronic. All AEs will be followed throughout the study until the Week 8 visit. All AEs related to the PINPOINT, SPY Elite or the surgical procedures, as determined by the Investigator, will be followed until resolution or deemed chronic.

At the final study visit, new AEs, as well as follow-up information for continuing AEs, will be recorded in the CRF and source document. If an SAE or UADE is unresolved at the final study visit, it will be followed by the Investigator until it resolves or becomes chronic (as judged by the Investigator). Follow-up data for such SAEs will be recorded in the source document and reported to the safety contacts. Non-serious ongoing AEs will be followed beyond the final study visit at the discretion of the Investigator.

## 9.6 Reporting of Technical Complaints/Device Deficiencies

### 9.6.1 Definitions

**Device Complaint:** A quality complaint received in writing, electronically, or orally that alleges deficiencies related to the identity, quality, durability, reliability, safety, effectiveness, or performance of a device product. (In this definition, "effectiveness" refers to the actual function of the device, not to how the subject responds to the action of the device. Also in this definition, "device product" refers only to devices provided by the Sponsor for clinical studies and to investigational devices.)

In this definition, safety includes the safety of a subject, user, or other person associated with the use of a medical device.

**Device Deficiency:** Inadequacy of a medical device with respect to its identity, quality, durability, reliability, safety or performance. Device deficiencies include malfunctions, use errors and inadequate labeling.

### 9.6.2 Reporting Procedures

Any technical complaint/device deficiency should be reported to the Sponsor. Technical Complaints occurring in this study must be reported immediately (within 24 hours) by fax or email to the appropriate Novadaq representative or to Novadaq Quality ([[contact]](mailto:[contact])).

Any complaint about a device must be reported regardless of whether the defect or deficiency had any effect on a subject or on study personnel.

## 9.7 ADEs, Technical Complaints/Device Deficiencies that are UADEs

Novadaq will evaluate all ADE reports and technical complaints/device deficiencies to determine if the report meets the definition of an unanticipated adverse device effect. If Novadaq determines that it does meet the definition, an investigation will be begun immediately. Novadaq will inform the Investigator of any additional reporting requirements beyond those stated in Sections 9.3 and 9.7 as applicable.

Novadaq will report the UADE and the results of any investigations to the FDA. All participating Investigator(s) will submit the required reports to their IRBs within 10 working days after Novadaq first received notice of the effect.

## 10 STATISTICAL CONSIDERATIONS

### 10.1 Primary Objective

To demonstrate an improvement in post-operative anastomotic leak rate in low anterior resection procedures where colon and rectal tissue perfusion is evaluated using PINPOINT or SPY Elite near infrared fluorescence imaging as an adjunct to standard surgical practice compared to surgical procedures performed according to standard surgical practice alone.

### 10.2 Hypotheses

$$\begin{aligned} H_0: & \quad p_t = p_c \\ H_1: & \quad p_t < p_c \end{aligned}$$

Where  $p_t$  and  $p_c$  represent the expected population incidences of post-operative anastomotic leaks in the treatment (PERFUSION) and control groups, respectively. Within their respective treatment groups,  $p_t$  and  $p_c$  will be estimated as the number of subjects who experience a post-operative anastomotic leak according to the definition in Section 3.1, divided by the number of subjects who either are included in the numerator or are known to be free of such leaks as of the 8 weeks visit. Subjects without a known anastomotic leak but with less than 6 weeks of follow-up (i.e., insufficient follow-up to declare them "leak-free") will not be included in these estimates.

### 10.3 Statistical Analysis

Analysis of these hypotheses will be conducted using a z-test (i.e., normal approximation to the binomial distribution, using a pooled variance estimate and without continuity correction), using a (one-sided) significance level of 0.025.

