**Sample Size and Statistical Analysis:**

The PILLAR III study is designed to allow a single mid-trial reassessment of sample size, employing the method of Mehta and Pocock. A minimum of 450 and a maximum of 1000 subjects will be enrolled at up to 30 centers. The trial will utilize a group sequential design with Pocock stopping boundaries with a planned sample size of 800 subjects. A futility boundary will also be incorporated. A single interim analysis will be conducted on the first 450 subjects enrolled with assessment of the primary endpoint. If the stopping boundary for trial success is not met at this interim analysis point and futility is not declared, the Mehta and Pocock method of sample size re-estimation based on promising zones will be applied to evaluate whether an increase in sample size above the planned 800 subjects is warranted (up to a maximum of 1.25 times the original planned sample size, i.e. 1000 subjects).

At the time of the interim analysis, the primary objective null hypothesis will be tested against the one-sided alternative hypothesis that the anastomotic leak rate in the PERFUSION arm is less than that experienced with the STANDARD surgical approach. If the p-value is less than a pre-specified threshold based on the Pocock stopping boundary, the null hypothesis will be rejected, whereas if the p-value is greater than the futility threshold, the trial will be considered futile. In either of these eventualities, no new enrollments will occur, and follow-up will only continue per regulatory requirements. However, if the p-value falls between these two thresholds, an evaluation of conditional power will be made to determine if a re-estimated larger sample size is warranted. The trial will then continue to either the planned sample size of 800 subjects or the re-estimated sample size of up to a maximum of 1000 subjects.

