### 10.4 Adaptive Design and Sample Size Considerations

Available literature does not provide a precise estimate of the expected anastomotic leak rate in the control group or in the treatment group. As previously described, anastomotic leak is reported to occur in a wide range of 3-20% of the time in colorectal surgery and the risk increases for lower anastomoses. In the limited prior experience with the PINPOINT PILLAR II study (n=139 subjects) the anastomotic leak rate was 1.4%.

Given the limited knowledge of control incidence and the treatment effect size, the PILLAR III study will employ an adaptive design with a mid-trial sample size re-assessment. The planned sample size is  $N = 800$ , with possible early stopping for efficacy or futility at an interim analysis at  $N = 450$ . The planned total of 800 subjects will provide >80% power to test the one-sided hypothesis of superiority for treatment over control in leak rate at the 0.025 significance level if the true leak rates  $p_c$  and  $p_t$  are 12.5% and 6.25% (a 50% relative reduction), assuming a two-look group sequential analysis plan (with Pocock alpha-spending bounds and analyses at 450 and 800). If the trial does not stop at  $N = 450$ , sample size will be assessed at that time and possibly increased up to a maximum of 1000 subjects, using the method of Chen et al. and described in Mehta and Pocock.

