For the primary objective, the following analysis plan will be used After  $N = 450$  subjects have been enrolled, randomized and treated and the primary outcomes observed. The primary objective null hypothesis will be tested against the one-sided alternative hypothesis above. If  $p < 0.0169$  (as determined by the Pocock alpha spending function), the null hypothesis will be rejected, whereas if  $p \geq 0.4$ , the trial will be considered futile. However, if  $0.0169 \leq p < 0.4$  an assessment of whether to increase the sample size above the planned 800 subjects will be made in accordance with the “promising zone” method of Mehta and Pocock. If the conditional power (CP) at  $N = 800$  subjects based on the available data at the time of the interim analysis is less than 0.5 or at least 0.8, enrollment will continue to 800 subjects and the final analysis will be conducted. Alternatively, if  $0.5 \leq CP < 0.8$ , the sample size will be re-estimated in accordance with the Mehta and Pocock method for sample size re-estimation up to a maximum of 1000 subjects. (The recalculated sample size cannot be less than 800 subjects based on the interim analysis.) The final sample size is calculated by determining the added sample size needed to achieve the target conditional power of 80% given the data at the time of the interim analysis, subject to a maximum of 1000 subjects. This method guarantees control of the type I error while still allowing standard inferential methods of analysis.

**10.5 The planned sample size 800 . is based on the following rationale: If the true leak rates  $p_c$  and  $p_t$  are 12.5% and 6.25% (a 50% relative reduction), respectively, then PASS 13 indicates that , a two-look group sequential analysis plan (with Pocock alpha-spending bounds and analyses at 450 and 800) achieves 81.6% power to reject the null hypothesis at a one-sided significance level of 0.025. Study Populations for Analysis**

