## 10.7 Secondary Objectives

The planned secondary objectives are listed below; they will be formally analyzed only once (at the interim analysis if the primary objective is passed at that time, or at the final analysis if the primary objective is not passed at the interim analysis). Data from these secondary objectives will not be included in the sample size re-assessment that occurs at the time of the interim analysis. The following objectives are intended to support product labeling. They will be tested in sequential fashion. I.e., if and only if the primary objective passes according to the criteria in Section 10.5 (which has a type I error rate of 2.5%), testing will proceed to the first secondary objective below (proportion of PERFUSION arm subjects in whom the PINPOINT or SPY Elite system provided sufficient visualization for assessment of blood flow and related tissue perfusion during the procedure). If and only if that objective passes, testing will proceed to the second secondary objective (incidence of abscess requiring surgical management). The standard for “passing” the secondary objectives will be a p-value less than 0.025 one sided.

To evaluate the ability of the PINPOINT or SPY Elite system to provide sufficient visualization for assessment of blood flow and related tissue perfusion during the procedure.

The statistical threshold for study success will be sufficient visualization for assessment of blood flow and related tissue perfusion in greater than 90% of subjects. Letting  $p_t$  represent the PERFUSION-group proportion of subjects for whom there was sufficient visualization for assessment of blood flow and related tissue perfusion, the following hypotheses will be tested:

H0:  $p_t \leq 0.9$

H1:  $p_t > 0.9$

The statistical test will be a one-sided exact binomial test of proportions. Descriptive statistics and 95% confidence intervals will be calculated for  $p_t$ .

To evaluate the effectiveness of assessing perfusion of colon and rectal tissue using PINPOINT or SPY Elite in reducing the incidence of post-operative abscess requiring surgical management.

Letting  $p_t$  and  $p_c$  respectively represent the treatment-group and control-group incidence of post-operative abscess requiring surgical management, the following hypotheses will be tested:

$$H_0: p_t = p_c$$

$$H_1: p_t < p_c$$

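### The primary test is printed at one-sided 0.025 with no final-look level: the planned look at 450 implies 0.0132 at N = 800, and the SAP does not say whether that look was made

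*Protocol*

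**What the plan says.** - Protocol 10.3 gives the primary test as a pooled-variance z-test without continuity correction, "using a (one-sided) significance level of 0.025". It mentions no looks. SAP 6.1 repeats the same test and level.
- Protocol 10.4 sets the power "assuming a two-look group sequential analysis plan (with Pocock alpha-spending bounds and analyses at 450 and 800". At 450 subjects the threshold is p < 0.0169, "as determined by the Pocock alpha spending function), the null hypothesis will be rejected"; p of 0.4 or more is futility. For the final analysis it gives no threshold.
- The sample size rationale, printed under the number 10.5, says the two-look plan "achieves 81.6% power to reject the null hypothesis at a one-sided significance level of 0.025", at leak rates of 12.5% and 6.25%.
- Protocol 10.7 opens the secondary tests only if the primary passes by "the criteria in Section 10.5 (which has a type I error rate of 2.5" percent).
- The Protocol Summary words the boundary differently: "The trial will utilize a group sequential design with Pocock stopping boundaries with a planned sample size of 800 subjects".
- SAP 3.1 and 3.3 replace the planned N with everyone enrolled through March 31, 2017. The SAP describes no interim look and does not state that none took place.

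**The concern.** The sentences that name the test and its threshold (10.3 and SAP 6.1) give 0.025 without calling it the overall level of a two-look plan. An analyst who follows them literally would compare the final p-value with 0.025. If 0.0169 had already been spent at 450, total error would exceed the 2.5% stated in 10.7. The level that should apply is printed in neither document and has to be solved for. At stake is the primary success decision, and with it access to the secondary tests meant to support labelling.

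**Working it through.** **Inputs.** Overall one-sided level 0.025, looks at 450 and 800, Pocock alpha spending, interim level 0.0169, leak rates 12.5% and 6.25% (Protocol 10.4 and the sample size rationale); 1:1 allocation (5.1); pooled z-test without continuity correction (10.3). No dropout, as in the stated power. Futility is ignored unless noted.

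**1. Reproduce the interim level.** Information fraction t = 450/800 = 0.5625. Spending: 0.025 × ln(1 + (e − 1)t) = 0.025 × ln(1.9665) = 0.01691, so z1 = 2.122. This matches the printed 0.0169.

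**2. Solve for the final level.** Under the null, the two z-statistics have correlation √0.5625 = 0.75. Solving P(Z1 > 2.122) + P(Z1 ≤ 2.122, Z2 > c) = 0.025 leaves 0.025 − 0.0169 = 0.0081 for the second term and gives c = 2.220, p = 0.0132. If the futility rule is treated as binding, the level is 0.0133.

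**3. Check it against the stated power.** Mean leak rate 0.09375; variance of the difference at 400 per arm = 2 × 0.09375 × 0.90625 / 400 = 0.0004248, standard error 0.02061. The final z has mean 0.0625 / 0.02061 = 3.032, and the interim z has mean 3.032 × 0.75 = 2.274. Power with candidate rules:

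| Interim level | Final level | Power |
|---|---|---|
| 0.0169 | 0.0132 | 81.6% |
| 0.0169 | 0.0169 | 83.7% |
| 0.0169 | 0.025 | 86.9% |
| 0.0151 | 0.0151 (constant Pocock bound) | 82.5% |

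Only the first row gives the printed 81.6%. The last row also fails to match the printed 0.0169.

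**4. Error if 0.025 is used at the final look.** The integral in step 2 with c = 1.96 gives 0.0345 at N = 800 (0.0341 with binding futility). A binomial simulation with 9.375% leaks in both arms gave 0.0347, against 0.0254 with a final level of 0.0132. The SAP fixes no N. The same integral with correlation √(450/N) gives 0.028, 0.031 and 0.033 at N = 500, 600 and 700, where the levels that restore 0.025 are 0.0210, 0.0166 and 0.0145. With no look, error at 0.025 is 0.025.

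**5. What changes in a result.** At 400 per arm with 50 control leaks:

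| Perfusion-arm leaks | One-sided p | Passes at 0.0132 | Passes at 0.025 |
|---|---|---|---|
| 31 | 0.0130 | yes | yes |
| 32 | 0.0179 | no | yes |
| 33 | 0.0244 | no | yes |

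**6. Conditional power needs the same bound.** Protocol 10.4 continues to 800 if conditional power "based on the available data at the time of the interim analysis is less than 0.5 or at least 0.8", but names no final bound. At the current trend, conditional power is Φ((z1 × 800/√450 − c√800)/√350). With c = 2.220, the zone from 0.5 to 0.8 covers interim p from 0.0186 to 0.0479. With c = 1.96 it would cover 0.0295 to 0.0708.

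**The case against.** The strongest reply is that the protocol, read whole, is not ambiguous. Section 10.4 attaches 0.025 to the two-look plan and claims type I error control, and 10.7 gives the primary criteria a 2.5% error rate. The missing level is therefore derivable, as the check shows. This stands, and it makes the protocol part minor. It does not excuse leaving a confirmatory threshold to be solved for while the sentence that defines the test shows a different number.

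Second, the SAP describes a single analysis, for which 0.025 is correct. This stands too, if no leak-rate comparison was made. Under 10.4 the look comes only after 450 subjects have outcomes, and the documents do not give the number enrolled.

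Third, Protocol 13.3 refers boundaries and stopping rules to a separate committee charter. A final level may be printed there, so the omission is claimed only for these two documents.

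A reader might also infer more than the documents support:

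- *That 0.0169 applies at both looks*, from the Summary's boundary wording. Section 10.4 specifies spending, and 83.7% contradicts the printed 81.6%. This needs only a wording alignment.
- *That conditional power uses z = 1.96.* Only 2.220 fits the stated 2.5%. The bound should be named, but the wider contrast describes a misreading.
- *That the abscess test needs look-specific levels*, because the secondary objectives are such that "they will be formally analyzed only once (at the interim analysis if the primary objective is passed at that time". At the design effect its error is about 0.026 for assumed correlations with leak of 0.5 to 0.9 (not in the documents), taking the visualization gate as passed. Stricter levels would cut an 80% power to about 75% (0.0169) or 72% (0.0132). That change is optional.

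**Conclusion.** The point holds as a conditional one. Neither document prints the final-look level. For looks at exactly 450 and 800 with non-binding futility it is 0.0132, and the protocol's own 81.6% power confirms it. If the planned look was made and the final test used 0.025, one-sided type I error would be 0.0345 at N = 800 instead of 0.025, with a smaller excess at a smaller final N. If no interim leak-rate comparison was made, there is no inflation.

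A reader might conclude that the trial's error rate is in fact inflated. The documents do not support that, because they do not say whether a look took place. Confidence is high in the omission and in the derived level, and none is claimed for actual inflation. The protocol text is a minor matter. The SAP's unqualified 0.025, with its silence on a look, should be fixed.

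**What to change.** 1. **Protocol 10.3 and 10.4.** State that 0.025 is the overall one-sided level. Print p < 0.0169 at N = 450 and p < 0.0132 (z > 2.220) at N = 800, to be recomputed from the spending function if the actual looks differ. State that conditional power at N = 800 uses this final bound. Align the Summary's boundary wording with 10.4.
2. **SAP 6.1.** State whether an interim comparison of leak rates was made. Use 0.025 only if none was; otherwise use the final level derived from the actual looks.

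The cost is a few sentences in each document. No stated primary power is lost, because 81.6% already assumes the stricter final bound.
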